### 9.2 Statistical Analysis Methods

#### Statistical Considerations

Patients will be enrolled to the study for Five years and followed for an additional year, by which time we expect most disease-related analytic events will have occurred. The design objectives will be different for the four subgroups: (1) Stage I PFH patients (stratum 1) with AFP  $\geq$  100 ng/mL or AFP not obtained prior to surgical resection of tumor; (2) low risk patients (stratum 2) defined as patients with Stage I non-PFH, non-SCU; Stage II non-SCU (3) intermediate risk patients (stratum 3); and (4) Stage IV patients or patients with AFP < 100 ng/mL at diagnosis (stratum 4). EFS will be the time from patient enrollment until last follow-up or an analytic event is observed, whichever comes first. Analytic events are: (1) progression of existing disease or occurrence of disease at new sites; (2) treatment failure defined as the presence of disease after four cycles of chemotherapy and post-induction surgery (if attempted) for patients enrolled with Stage III disease or presence of disease after planned chemotherapy (eight cycles for non-responders, ten cycles for responders) for patients enrolled with Stage IV disease (3) death from any cause prior to disease progression or diagnosis of a second malignant neoplasm; or (4) diagnosis of a second malignant neoplasm. Survival will be the time from enrollment until death from any cause or last follow-up, whichever comes first.

[Section 3](#) requires that planned start of systemic therapy for patients whose protocol prescribed therapy includes chemotherapy must be within 42 days of enrollment. Experience from prior COG studies of hepatoblastoma demonstrates that this can be accomplished in most patients. All patients who die within 42 days of enrollment will be considered in the analytic plans below. All patients who survive more than 42 days after enrollment and whose protocol therapy prescribes chemotherapy but who do not have such systemic therapy started by the 43rd day after enrollment will be excluded from the analyses below.

A patient enrolled without histological confirmation (see [Section 3.2.2.b](#)) will be considered evaluable for all study analyses unless the tumor tissue obtained in a future surgical procedure is not consistent with hepatoblastoma or reveals another pathological diagnosis. If histological confirmation is not confirmed in the future for these patients by a biopsy or surgical resection, they will be considered off study.

The statistical analysis will include an assessment of the influence of the exclusion of cases for whom there is a discrepancy in diagnosis between institutional and central review, or for whom there is an atypical histological presentation. The influence will be assessed by comparing the EFS and survival, as estimated by the method of Kaplan and Meier with and without such cases. This will provide an *ad hoc* assessment of the effect of such cases on outcome characterization. Formal statistical quantification of such effects will not be straightforward.

Surgical resection followed by observation was first tested on COG trial P9645 and has been demonstrated to be a successful approach for patients with stage I PFH. These patients will be enrolled on the trial, since

it will be necessary to submit all Stage I and II patients to mandatory central review to determine the appropriate analytic strategy. The results of this review will be returned for information to the relevant institutional investigator. Individuals considered Stage I PFH and treated with surgery only will be considered for the analysis described in the paragraph below. Individuals considered Stage I non-PFH, non-SCU, Stage II, non-SCU patients and treated with the chemotherapy for such patients will be considered in the analysis described in "[Hypothesis 1.1](#)" below.

[figure not shown]
Nine (9) stage I PFH patients will be required for AHEP0731. We may enroll up to 12 patients to account for patients who are determined later to be ineligible. These patients will be followed closely for disease and life status. The outcome of these patients will be summarized through survival and EFS curves estimated by the method of Kaplan and Meier. If 2 or more analytic events are observed, the strategy of surgery without any further therapy will identify enrollment to this strategy for possible termination because of insufficient disease control. If this strategy is associated with a long-term event-free survival of 65%, the probability of accepting it is 0.12. If this strategy is associated with a long-term event-free survival of 93%, the probability of accepting it is 0.89.

Toxicity will be reported using CTCAE criteria (version 4). All Grade 3 or 4 or greater non-hematological toxicities as well as any toxicity that requires submission of an CTEP-AERS report as outlined in protocol [section 11.3](#), Table B, will be reported while the patient is on protocol therapy. The frequency of each toxicity type will be quantified as the percent of reporting periods on which the toxicity of the relevant grade is reported. All reporting periods where the patient receives at least one dose of each of the agents in the therapeutic plan for that individual will be included in the denominator for the rate calculation.

Follow-up data will be obtained on all patients considered eligible for the protocol. As part of the study design, slides sufficient to confirm the histological subtype of hepatoblastoma (PFH v. SCU v. neither PFH nor SCU) of all Stage I patients will be submitted to mandatory central review according to the time lines described above. Patients for whom the central review supports the therapeutic approach of the institutional investigator will constitute the analytic subgroup for each of the analyses planned for Stage I patients. The results of this review will be returned for information to the relevant institutional investigator as soon as the assessment becomes available in the COG data system.

Hypothesis 1.1: (Stage I, non-PFH, non- SCU, Stage II, non-SCU [Stratum 2]): Expected Annual Accrual: 9.2 patients per year. Total: 51 patients. We may enroll up to 60 patients to account for patients who are determined later to be ineligible.

If 7 or more analytic events are observed the strategy of surgery with reduced chemotherapy will identify enrollment to this strategy for possible termination because of insufficient disease control. If this strategy is associated with a long-term event-free survival of 78%, it will be rejected with probability 0.90. If this strategy is associated with a long-term event-free survival of 89%, it will be accepted with probability 0.81. The graph below describes the probability of accepting the strategy as a function of its long-term EFS:

Hypothesis 1.2 (Intermediate-risk patients [Stratum 3]): As of Amendment #3B enrollment to stratum 3 is terminated because sufficient patients have been enrolled to address the hypothesis. The total enrollment to stratum 3 was 105 patients.

*Feasibility of Delivery of C5VD*: The primary measure of feasibility will be rate of death as a first analytic event. All patients who receive at least one dose of the C5VD regimen will be considered evaluable for this endpoint. Any patient who dies on protocol therapy or within 30 days of the termination of protocol therapy of a cause considered possibly, probably or likely related to systemic chemotherapy will be considered to have experienced an on-protocol-therapy death. If five or fewer of the 99 patients experience on-protocol-therapy death, the regimen will be considered feasible for further development. If the regimen is associated with a death-event rate of 3%, that observed for patients who were assigned to chemotherapy on P9645, the regimen will be considered feasible with probability 0.92. If the regimen is associated with a death-event rate of 10%, the regimen will be considered not feasible with probability 0.94. If the sixth on-protocol-therapy death is reported, study enrollment will be suspended. In addition to this, at each report to the DSMC the estimated on-protocol-therapy death rate and its 95% confidence interval will be reported to the phase III DSMC as the cumulative incidence of on-treatment death and the 95% confidence intervals at four and six months.

Since the addition of doxorubicin to C5V may affect the delivery of all the agents in the combination, we will characterize the amount of each agent that can be delivered during the first four cycles of therapy and the actual amount of doxorubicin delivered on protocol therapy. During the first four cycles, the total dose of each agent administered will be collected, along with the patient's height and weight. The average amount of each drug, calculated as dose per meter squared will be calculated and a lower 95% confidence bound on the true average dose delivered will be calculated assuming a normal distribution of delivered dose. In addition the total doxorubicin dose, in milligrams per meter squared will be calculated for each patient as well as the average and the 95% confidence interval for this amount. This will be used in planning subsequent trials.

Hypothesis 1.3: (Stage IV [Stratum 4]): Expected Annual Accrual: 16 patients per year. Total: 43 patients (to account for patients who may be later determined to be ineligible.)

Prior to Amendment 3B, VI therapy was evaluated in stage IV patients. No patient assigned to VI experienced early progression. All patients evaluated for the VIT combination, therefore, will be evaluated only for response as defined in Section 10 of the protocol.

[figure not shown]
Disease status at the end of two cycles of therapy (or earlier in the case of early progressive disease) will be the endpoint for evaluable patients.

A patient will be considered evaluable if the individual is eligible, receives at least one dose of each agent in the combination being tested and is not removed from protocol therapy for reasons other than toxicity or disease progression. Any evaluable patient who has a CR or PR according the criteria prescribed [Section 10](#) of the protocol will be considered a 'responder'. All other evaluable patients will be considered non-responders. Patients will be enrolled in two stages according to the design specified below:

Number of Evaluable Patients Enrolled	Results	Decision
Stage I: 22 Evaluable Patients	9 or fewer responders	Terminate the trial with the conclusion the regimen does not demonstrate sufficient disease control
	10 or more responders	Continue to the next stage and enroll 19 more patients
Stage II: 19 Evaluable Patients (Total of 41)	Cumulatively 22 or fewer responders	Terminate the trial with the conclusion the regimen does not demonstrate sufficient disease control
	23 or more responders	Terminate the trial with the conclusion the regimen demonstrates sufficient disease control for further investigation

The statistical characteristic of this rule are presented in the figure below:

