#### 2.3.4 High-Risk Patients

High-risk patients include: 1) any patient with metastatic disease; 2) any patient with a low diagnostic AFP level < 100 ng/mL, regardless of stage (see [Section 7.1](#)).

Based on multiple cooperative group studies, the 40-70% EFS for unresectable patients and 20-40% EFS for metastatic patients remain suboptimal (see Table 2). The optimal dose of cisplatin to administer to patients with unresectable and metastatic disease is unclear. However, as cisplatin is the most active agent for hepatoblastoma, intensification of cisplatin therapy may be beneficial. The dose of cisplatin proposed for intermediate- and high-risk patients in this trial exceeds doses used in other trials. SIOPEL administers an additional 3 grams of platin-based therapy with carboplatin to patients who receive 320 mg/m^2 of cisplatin. SIOPEL-4, the current study for high-risk patients includes cisplatin (570 mg/m^2), doxorubicin (300-350 mg/m^2) and 2-3 courses of carboplatin. The HB studies administer 12,000 mg/m^2 of ifosfamide. Table 3 provides a dose comparison of the cumulative chemotherapy dosing for intermediate- and high-risk patients being used in current studies.

Table 3. Cumulative Dosage\* of Chemotherapy in Advanced-Stage Patients According to Treatment Regimen

Study	CDDP	DOXO	IFOS	CARBO	VCR	FU
AHEP0731	600	360	0	0	33-39	3600
P9645	600	0	0	0	0	0
SIOPEL-2	320	360	0	3000	0	0
SIOPEL-4	570	300-350	0	2-3 courses	0	0
HB-GPOH	400	240	12000	0	0	0

\*Chemotherapy dosing is mg/m^2

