### 4.1 Overview of Treatment Plan

AHEP0731 builds on the results of the last 20 years of hepatoblastoma clinical trials and seeks to diminish toxicity in the approximately 30% of low-risk patients, increase survival in intermediate-risk patients and identify new agents(s) that may be used in high-risk and recurrent patients.

All patients with Stage I PFH hepatoblastoma will be classified as very low-risk (Stratum 1) and will be treated with surgery only. Patients with Stage I non-PFH, non-SCU hepatoblastoma or with Stage II non-SCU hepatoblastoma will be classified as low-risk (stratum 2) and will be treated on Regimen T with 2 adjuvant cycles of cisplatin, 5-fluorouracil, and vincristine (C5V), a reduction from the standard 4 cycles of chemotherapy given on previous COG trials. Patients with Stage I SCU, Stage II SCU, or any Stage III hepatoblastoma will be classified as intermediate-risk (stratum 3) and will be treated with Regimen F (intermediate risk, stratum 3, has been closed to accrual as of 03/12/12). This treatment regimen is based on previous COG trials that administered 6 cycles of C5V therapy plus surgical resection of the tumor. However, to improve resection and survival rates, doxorubicin, an agent with proven efficacy will be added to the C5V therapy (C5VD). All patients with any Stage IV hepatoblastoma as well as patients with any stage of hepatoblastoma and initial AFP < 100 ng/mL will be classified as high-risk (stratum 4).

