#### 4.5 Treatment for Intermediate-Risk Patients (Stratum 3 - Regimen F)

**Note: Stratum 3 has been closed to accrual as of 03/12/12.**

All patients with Stage I SCU, Stage II SCU, and Stage III disease will be treated with Regimen F (C5VD). Patients will receive 4 cycles of therapy repeated every 21 days, followed by surgical resection of the tumor or liver transplant (OLT). Patients whose tumors are removed surgically or by OLT after Cycle 4 will receive 2 post-operative cycles of chemotherapy. Patients may have their tumor removed if deemed feasible after 2 cycles of chemotherapy but will then receive 4 cycles of post-operative chemotherapy. **All intermediate-risk patients will receive a total of 6 cycles of chemotherapy.** Patients whose tumors remain unresectable after 4 cycles will be considered off protocol therapy, but will continue to be followed on the AHEP0731 off protocol therapy follow-up CRF. These patients can at the discretion of the primary physician. Additional pre-operative cycles of chemotherapy after Cycle 4 are **NOT** permitted in an attempt to make the tumor resectable or if a liver is not available for transplantation. Patients with progressive disease at any time are off-protocol therapy.

Tumors that are unresectable at diagnosis should be referred to a surgical center with expertise in pediatric liver transplant and “extreme” liver resection as soon as possible. Optimally for planning purposes, this liver transplant consultation should be obtained but at the latest it should be done following the first 2 cycles of neoadjuvant chemotherapy. The consent for the PLUTO registry should be obtained within one month of undergoing liver transplant and is usually obtained by the liver transplant team.

For the purposes of this study, consultation will be defined and may be accomplished in one of two ways:

- The FIRST TIME the patient is seen face to face by the transplant physician/team in the same institution or another institution.
- The FIRST TIME radiographic films and referral material are sent to the transplant physician/team at the same or another institution and are formally reviewed by the transplant physician/team.

The transplant physician/team will communicate the result of this consultation back to the referring physician.

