#### 4.6 Treatment for High-Risk Patients (Stratum 4) - Regimen H

All high-risk patients will receive 2 cycles of vinCRiStine, irinotecan and temsirolimus (VIT), using a 5 day irinotecan schedule, as “up-front” window therapy on Regimen H. Each cycle lasts 21 days and cycles will start on Weeks 1 and 4. Antibiotics will be given to patients receiving irinotecan who develop chemotherapy-related diarrhea. See “Diarrhea Secondary to Irinotecan” in the Supportive Care Guidelines at: <https://members.childrensoncologygroup.org/prot/reference materials.asp> under Standard Sections for Protocols.

Following 2 cycles of VIT, patients will be evaluated for response (see [Section 10.3](#)). The assessment of response is based on central review of imaging, the alphafetoprotein values and sampling dates. The results of the central review will be returned to the institutional investigator within 3 weeks of submission of the imaging and AFP material. If there is a discrepancy between the assessment by central review and by institutional assessment, the study PI will discuss with the treating physician to resolve the discrepancy. If the investigator selects a post-induction regimen that is *not* indicated by the central review of response, the patient will be considered off protocol therapy as of the start date of consolidation therapy.

Patients who *respond* (demonstrate a complete or partial response) to VIT will then receive a total of 6 cycles of C5VD therapy and 2 more cycles of VIT. Following first 2 cycles of VIT, no further VIT should be given until after surgical resection/liver transplant to avoid potential surgical complications of thrombosis and wound dehiscence. Each cycle lasts 21 days. A total of 10 cycles of chemotherapy (6 cycles of C5VD and 4 cycles of VIT, including the “up-front” window therapy) will be given. VIT is intended to be given during Cycles 7 and 10. However, the order of chemotherapy cycles can be switched at the discretion of the treating oncologists and surgeons to optimize surgical outcomes and minimize complications.

Patients who *do not respond* to VIT will continue with 6 cycles of C5VD repeated every 21 days and receive no further VIT. A total of 8 cycles of chemotherapy (6 cycles of C5VD and 2 cycles of VIT, including the “up-front” window therapy) will be given.

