Tumors that are unresectable at diagnosis, even if metastatic disease is present, should be referred to a surgical center with expertise in pediatric liver transplant and “extreme” liver resection should be done as soon as possible. Optimally for planning purposes, this liver transplant consultation should be obtained at diagnosis and no later than the FIRST DAY of the 3rd cycle of C5VD chemotherapy. The consent for the PLUTO registry should be obtained within one month of liver transplant and usually is obtained by the liver transplant team.

For the purposes of this study, consultation will be defined and may be accomplished in one of two ways:

- The FIRST TIME there is documented telephone or email/letter contact and a request for consultation between the treating oncologist and the liver specialty/transplant team.
- The FIRST TIME radiographic films and referral material are sent to the transplant physician/team at the same or another institution and are formally reviewed by the transplant physician/team.

The liver specialty/transplant physician/team will communicate the result of this consultation back to the referring physician.

Resection planning is to be completed before completion of the 4th cycle of C5VD chemotherapy. See Surgical Guidelines in [Section 13.0](#).

Patients will be evaluated after every 2 cycles of C5VD chemotherapy that occur prior to resection. Patients may have their primary tumor removed whenever it is feasible. It is the intent of the treatment that patients should have their tumors removed surgically or by OLT at the latest after Cycle 6 in both responders and

non-responders (ie, after the 4th cycle of C5VD) so that they can receive post-operative cycles of chemotherapy.

Chemotherapy should resume as soon as possible after surgical resection. In most circumstances this can typically be achieved within 3 weeks following surgery. **Patients who do not resume post resection chemotherapy within 42 days of resection will be considered off protocol therapy but not off study.** Further treatment will be at the discretion of the treating physician. Patients will continue to be followed on the AHEP0731 off protocol therapy follow-up CRF.

Regardless of the timing of surgery, patients should receive the total number of cycles as described above.

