**Patients whose tumors remain unresectable at the completion of planned therapy will be considered to have experienced an adverse EFS event. No further protocol therapy is planned for such patients. These patients can be treated at the discretion of the primary physician.**

Patients with pulmonary metastases will receive the first 2 cycles of Regimen H chemotherapy described above. If metastases disappear with chemotherapy, no pulmonary surgical intervention will be performed. If metastases are persistent after 4 total cycles of C5VD chemotherapy and the patient is considered a candidate for liver transplant at that time, metastases are to be resected to render the patient free of extrahepatic disease prior to transplant. Transplant may then be undertaken. If the liver tumor can be primarily resected after either 2 or 4 cycles of C5VD chemotherapy without transplant, this should be performed and the final cycles of chemotherapy should be administered. If the metastases are still present, they should then be resected. Pulmonary metastectomy may be performed earlier in the course of therapy if it can be done without resulting in delays in the administration of scheduled chemotherapy.

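### The EFS treatment-failure event in Section 9.2 is keyed to enrolment stage, so Stage III patients with AFP below 100 ng/mL on Regimen H or W fall under a four-cycle rule that conflicts with Section 4.6

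*Combined protocol and SAP*

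**What the plan says.** Section 9.2 lists treatment failure among the analytic events and splits it by stage. For Stage III it is "presence of disease after four cycles of chemotherapy and post-induction surgery (if attempted) for patients enrolled with Stage III disease". For Stage IV it is "presence of disease after planned chemotherapy (eight cycles for non-responders, ten cycles for responders) for patients enrolled with Stage IV disease". Neither limb mentions AFP, stratum or regimen, although the same paragraph defines Stratum 4 to include patients with AFP below 100 ng/mL.

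Section 2.3.4 places in the high-risk group "any patient with a low diagnostic AFP level < 100 ng/mL, regardless of stage". The table in Section 4.1 sends them to Stratum 4 and Regimen H, which replaced Regimen W at Amendment 3B.

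Section 4.6, which governs high-risk patients, has its own EFS rule: "Patients whose tumors remain unresectable at the completion of planned therapy will be considered to have experienced an adverse EFS event". It carries no stage condition. The same section intends that patients "should have their tumors removed surgically or by OLT at the latest after Cycle 6 in both responders and" non-responders.

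Section 8.1 removes patients from protocol therapy for unresectability by risk group: four cycles for intermediate risk, ten for high-risk responders and eight for high-risk non-responders.

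**The concern.** The four-cycle limb suits Regimen F, where Section 4.5 places surgery after four cycles of C5VD. A Stage III patient with low AFP is not on Regimen F. After four cycles on Regimen H that patient has had two window cycles and two of C5VD, with surgery possibly still ahead. Two sections then give different answers about when, and on one reading whether, the patient has had an event.

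The estimate exposed is EFS in patients with AFP below 100 ng/mL, which secondary aim 1.3.8 names. Aim 1.3.3 (2-year EFS around transplant referral) is exposed only if such patients are transplant candidates. An analyst programming from Section 9.2 and one programming from Section 4.6 could report different curves from the same data.

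**Working it through.** The documents attach no numerical figure to this clause, so the check compares the rules and counts cycles.

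**Inputs.** Cycles last 21 days (Section 4.6). All high-risk patients start with 2 VIT cycles. Non-responders then receive 6 C5VD; responders receive 6 C5VD and 2 more VIT.

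**Does the cycle count in 9.2 include the window?** Non-responders: 2 + 6 = 8. Responders: 4 + 6 = 10. These match the eight and ten in the Stage IV limb, so that sentence counts window cycles. On the same count, four cycles on Regimen H means 2 VIT + 2 C5VD.

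**Timing** (3 weeks per cycle, no delays, measured from the start of chemotherapy):

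| Point | Cycle | Week |
|---|---|---|
| Stage III limb of 9.2 | 4 | 4 × 3 = 12 |
| Latest intended tumor removal, Regimen H | 6 (4th C5VD) | 6 × 3 = 18 |
| 4.6 rule, non-responders | 8 | 8 × 3 = 24 |
| 4.6 rule, responders | 10 | 10 × 3 = 30 |

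The Stage III limb falls 18 − 12 = 6 weeks before the latest intended surgery point. It falls 24 − 12 = 12 or 30 − 12 = 18 weeks before the Section 4.6 event.

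**Stage III, AFP below 100, under each reading of 9.2:**

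| Patient | 9.2 read literally at Cycle 4 | 9.2 read as waiting for surgery | 4.6 |
|---|---|---|---|
| Clear of disease by Cycle 4 | no event | no event | no event |
| Resected clear after Cycle 5 or 6 | event, week 12 | no event | no event |
| Tumor never removed | event, week 12 | event, about week 12 | event, week 24 or 30 |

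The last row disagrees with Section 4.6 on both readings.

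**Stage I or II, AFP below 100.** Neither limb of 9.2 names these stages, so these Regimen H patients have no treatment-failure event there, while the Section 4.6 rule does cover them. Appendix III defines Stages I and II as at least grossly resected, so the practical consequence is probably small.

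**Size.** Let *f* be the share of the AFP-below-100 group who are Stage III with tumor still in place after Cycle 4, and *S* the EFS under the Section 4.6 rule, taken as equal in all. On the literal reading the estimate becomes (1 − *f*) × *S*, a drop of *f* × *S*. The documents do not give *f*, so 0.10 to 0.50 is an assumption. With *S* = 0.13, the 3-year EFS quoted in Section 2.4 for low AFP, the drop is 0.10 × 0.13 = 1.3 points to 0.50 × 0.13 = 6.5 points. With *S* = 0.50, also assumed, it is 5 to 25 points. On the waiting reading, event status at or beyond week 30 is the same for the patients tabulated above. Only the dates move.

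**What is not affected.** The Stratum 4 decision in Section 9.2 uses response. With X ~ Bin(22, *p*) and Y ~ Bin(19, *p*), the probability of acceptance is the sum over x = 10 to 22 of P(X = x) × P(Y ≥ 23 − x). This gives rejection 0.900 at 45%, acceptance 0.907 at 65%, and stopping at the first stage 0.435 at 45%. The plan states 0.90, 0.90 and 0.435. EFS does not enter. The Stratum 3 rule counts on-therapy deaths, and the Stratum 1 and 2 rules concern Stage I and II patients, whom neither limb mentions.

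**The case against.** The strongest reply is that the Stage III limb includes post-induction surgery if attempted. On Regimen F the operation follows Cycle 4, so the clause works there only if assessment waits for surgery. Read the same way on Regimen H, a patient resected clear after Cycle 5 or 6 is not a failure. This is a fair reading, and it stands. A reader might infer that the plan definitely scores on-schedule patients as failures before their operation and so makes low AFP look worse than it is. The documents do not support that as a certainty: it follows from the literal reading, which is not the only one.

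A second reply is that four cycles could mean four C5VD cycles. The eight and ten in the same sentence include window cycles, which tells against it. Even so read, an unremoved tumor would be dated at week 18, still 6 or 12 weeks before the Section 4.6 point.

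Third, Section 4.6 already holds the regimen-based rule, so this is a conflict between sections and not a missing definition. That is correct, and it is why the repair is small.

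Fourth, few patients may be involved. Projected Stratum 4 accrual is 16 of 3 + 9.2 + 41.6 + 16 = 69.8 per year, about 23%, while Section 2.3.4 puts metastatic disease alone at 25% of cases. That suggests a small group but does not show it is empty.

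**Conclusion.** The inconsistency is real. For a Stage III patient with AFP below 100 ng/mL whose tumor is never removed, no reading considered here brings Section 9.2 into line with Section 4.6. The event is dated about week 12 under one and week 24 or 30 under the other, assuming 21-day cycles without delay. For patients resected after Cycle 4, the two sections agree or disagree according to how the surgery qualifier is taken, so a directional bias in the low-AFP estimate is possible but not established. Stage I and II patients with low AFP are left without a treatment-failure clause in 9.2.

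The reach is limited to secondary EFS estimates: aim 1.3.8, and aim 1.3.3 if such patients are transplant candidates. The magnitude cannot be determined from the documents; the ranges shown above rest on assumed shares. The point should be corrected because the text is wrong as written, but it does not threaten any primary conclusion.

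**What to change.** Reconcile Section 9.2 with Sections 4.6 and 8.1 by keying the treatment-failure event to assigned regimen:

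- **Regimen F:** disease present after four cycles and any post-induction surgery.
- **Regimen H or W, whatever the stage:** disease present at completion of planned chemotherapy (eight cycles for non-responders, ten for responders).

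This settles the Stage III conflict and closes the Stage I and II gap. It changes only the event definition and leaves the treatment and surgical schedules as they are. The cost is one sentence, settled before the EFS analyses are run. No new data are needed, because Section 7.5 already schedules tumor evaluation after Cycles 4 and 6 and at the end of therapy. The report of aim 1.3.8 should give the number of AFP-below-100 patients by stage, so that readers can see how many the clause touches.
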